#### 690 **4.2.2. Participant Selection**

691 See Section 4. for eligibility criteria. For contemporaneous DDLT controls, the 692 following gives further details on patient selection.

693

694 The primary population of choice for recruiting DD controls would comprise those 695 individuals from the A2ALL Retrospective study who received deceased donor 696 transplants after 3/1/03. If there aren't enough candidates from this population, then the 697 following method will be utilized for identifying DD contemporaneous controls: 698 In each center, following any LD transplant, the next eligible DDLT recipient will be 699 approached at the time of identification of a donor (if they have not been previously 700 enrolled), until a DDLT is enrolled. The contemporaneous control recipient will undergo 701 all perioperative and post-transplant follow-up appropriate for the study. This step will 702 be repeated each time an LDLT is performed until the point when patients enrolled 703 prospectively in the cohort study who did not receive LDLT begin to be receiving DDLT 704 by virtue of progressing on the waiting list (we estimate this will take one to two years).

705

Throughout the period of enrollment in the cohort study, the numbers of LDLT and

707 DDLT will need to be comparable in each center. This will be verified by review of

enrollment conducted by Data Coordinating Center every 6 months. If enrollment of

DDLT falls below that of LDLT in any center during the study, the above procedure willbe used to correct the deficit of DDLTs.

711 **4.2.3. Data Elements** 

712 Recipient data collection:

- 713 1. Recipient Condition at Transplant
- 714 2. Recipient Intraoperative Data
- 715 o Liver biopsy
- 716 3. Recipient Post-Surgical Morbidity
- 717 4. Recipient Complication Severity
- 718 5. Recipient Hospitalization data
- 719 6. Recipient QOL Assessment
- 720 7. Recipient Survival
- 721

722

#### 4.2.4. Sample Size and Power Calculations

Estimation of proportions of donor complications will be made using 95% confidence
intervals (CI) based on the binomial distribution. Assuming 660 donors, 95% CI widths
will be no larger than +/- 0.04.

726

Comparisons of recipient complications after LDLT and DDLT transplants will be based
on chi-square tests of equality of proportions. Assuming n=660 LDLT, n=550 DD, and
alpha=0.05, we will have 83% power to detect a difference in the proportion of bile leaks,
for example, of 0.18 in the DDLT group versus 0.25 in the LDLT group (a difference of

731 0.07). Physician estimates of this difference are closer to 0.20, so power is more than

- 731 0.07). Physician estimates of this difference are closer to 0.20, so power is more than
   732 sufficient for this endpoint. If we more conservatively assume complication proportions
- near 0.5, we will have 93% power to detect a difference of 0.10 (such as 0.45 versus
- 734 0.55).

#### 735

For comparing hospitalization between LDLT recipients and non-recipients we consider the number of hospital days in one year. Although the analysis will take into account the possibility that some patients may be included in both groups, both pre- and post-LDLT, the power calculations consider a similar but simplified design based on a two-sample ttest (2-sided, alpha=0.05), assuming 660 LDLT recipients and 710 non-recipients. We have no preliminary data on means or standard deviations (s.d.s) for number of hospital days in a year, but assuming a fairly large s.d. of 25 days, we will have 95% power to

- days in a year, but assuming a fairly large s.d. of 25 days, we will have 95% power to detect a difference of 5 days (effect size = 0.20 s.d.) between LDLT and non-LDLT
- 744 groups.
- 745

746

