#### 572 **4.1.4. Sample Size and Power Calculations**

573 We will compare the survival experience between those who receive an LDLT and those considered for an LDLT but not receive one. Although the analysis will involve a fairly 574 575 complex method of matching LDLT recipients with sets of non-recipients, for the 576 purpose of power calculations, we will assume a much simpler 2-group design. For this 577 analysis, we will pool the patients from the Retrospective Study and the Cohort Study for 578 maximum power. We anticipate having at least 300 LDLT recipients and 500 non-LDLT 579 recipients from the Retrospective Study, and 360 LDLT and 710 non-LDLT from the 580 Cohort Study, for a total of 660 LDLT and 1210 non-LDLT recipient patients. Power 581 calculations are based on the (two-sided) logrank test, an exponential survival 582 distribution, approximately uniform accrual of patients for at least 7 years (from 1998) 583 with 3 additional years of follow-up, 1% loss to follow-up, and a significance level of 584 0.05. Assuming a one-year survival probability of 0.875 in the LDLT group, we have 585 90% power to detect as significant a one-year survival probability among non-recipients 586 lower than 0.85 or higher than 0.90.

[figure not shown]

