#### **4.3.4.** Sample Size and Power Calculations

907 This analysis is based on comparisons of donors and donor controls over time in the 908 standardized questionnaire scores. For the power calculations, we will consider the 909 power to detect differences between donors and controls at a single time point based on a 910 two-sample t-test. Power for the proposed repeated measures analysis will be greater, 911 although the amount of improvement will depend on the correlation between successive 912 measures on the same individual, which is not known at this time. We assume that the 913 Cohort Study will yield 360 LDLT donors and 710 donor controls

914

915 Assuming a 2-sided significance level of 0.05, we will have 87% power to detect an

916 effect size of 0.20 (i.e., a difference of 0.20 standard deviations in any given measure

917 between donors and donor controls). Cohen has suggested that an effect size of 0.25 is a 918 small effect, so we will have the power to detect quite small differences between donors 919 and donor controls.

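### The hospital-days power in Section 4.2.4 sets a pooled LDLT count (660) against a Cohort-only non-recipient count (710), so its 95% matches neither population the protocol defines

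*Protocol*

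**What the plan says.** Section 4.2.4 (Primary Aim 2) rests the hospital-days power on a t-test for two groups, two-sided at the 0.05 level, "assuming 660 LDLT recipients and 710 non-recipients". With an SD of 25 days it claims 95% power for this target: "detect a difference of 5 days (effect size = 0.20 s.d.) between LDLT and non-LDLT". It calls this a simplified version of the real analysis, in which a patient may contribute to both groups, before and after LDLT.

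Section 4.1.4 shows where the counts come from. For the Retrospective Study: "We anticipate having at least 300 LDLT recipients and 500 non-LDLT". For the Cohort Study: "and 360 LDLT and 710 non-LDLT from the" that study. The sum is given as "Cohort Study, for a total of 660 LDLT and 1210 non-LDLT recipient patients". Pooling is announced there for the survival analysis of Primary Aim 1; Section 4.2.4 does not say whether it carries over to hospitalization.

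Section 4.3.4, on donor quality of life, uses the same Cohort-only split: "Cohort Study will yield 360 LDLT donors and 710 donor controls". Section 4.6.4 (HCC) also pairs 710 with 360 as the Cohort Study counts.

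**The concern.** A power figure should describe the comparison that will be made. Here the LDLT group has the size it has only if the Retrospective Study is included, and the comparator has the size it has only if that study is left out. The 300 Retrospective LDLT patients are counted and the 500 Retrospective non-recipients are not, with no explanation.

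Resource utilization is a named part of Primary Aim 2. A reader who relies on the 95% cannot tell which patients it refers to, or whether it errs on the safe side.

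**Working it through.** **Inputs, all from the protocol**

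- Difference 5 days, SD 25, so effect size d = 5/25 = 0.20; two-sided alpha 0.05 (Section 4.2.4).
- Retrospective Study: 300 LDLT, 500 non-LDLT (Section 4.1.4).
- Cohort Study: 360 LDLT, 710 non-LDLT (Section 4.1.4).
- Pooled: 300 + 360 = 660 LDLT; 500 + 710 = 1,210 non-LDLT.

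**Formula** (normal approximation to the two-sample t-test)

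Power = Φ( d / √(1/n₁ + 1/n₂) − 1.96 )

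**Step 1: reproduce the stated figure, 660 against 710**

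√(1/660 + 1/710) = 0.05407; 0.20/0.05407 = 3.699; Φ(3.699 − 1.96) = Φ(1.739) = 0.959.

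The protocol states 95%, so its figure is reproduced.

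**Step 2: both groups pooled, 660 against 1,210**

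√(1/660 + 1/1210) = 0.04839; 0.20/0.04839 = 4.133; Φ(2.173) = 0.985.

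**Step 3: both groups from the Cohort Study, 360 against 710**

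√(1/360 + 1/710) = 0.06470; 0.20/0.06470 = 3.091; Φ(1.131) = 0.871.

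The noncentral t distribution gives 0.959, 0.985 and 0.870. Section 4.3.4 itself states 87% for a 360 against 710 split at 0.20 SD. That calculation concerns donors and donor controls, so it confirms the arithmetic but not the choice of population.

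**Step 4: difference detectable with 95% power**, (1.960 + 1.645) × 25 × √(1/n₁ + 1/n₂)

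| Groups | Power for 5 days | Difference at 95% power |
|---|---|---|
| 660 / 710 (as stated) | 95.9% | 4.87 days |
| 660 / 1,210 (pooled) | 98.5% | 4.36 days |
| 360 / 710 (Cohort only) | 87% | 5.83 days |

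Against the stated 95%, the pooled figure is 98.5 − 95 = 3.5 points higher and the Cohort-only figure 95 − 87 = 8 points lower.

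**The case against.** The best defence is that Section 4.2.4 leans towards pooling, so that the stated power is merely cautious. The section uses 660 throughout. Its complications calculation sets 660 LDLT against 550 DDLT, and 550 exceeds the 355 DDLT that Sections 4.5.4 and 4.8.4 expect in the Cohort Study. Section 4.2.1 defines the living donor group as every living donor transplant. On that view 710 should read 1,210 and power rises. This stands as a plausible reading, but it is not stated. Section 3.1, item 2, places the comparison of pre-transplant resource use in the overall cohort from enrollment, which can be read the other way. The mix might even be deliberate, for example if usable hospital data existed only for Cohort non-recipients, but the protocol does not say so.

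A second defence is that the count matters little beside the admitted lack of data on the SD. Keeping 660 against 710 and raising the SD to 30 gives 0.1667/0.05407 = 3.08 and Φ(1.12) = 87%, the same as the Cohort-only figure. That is fair and limits the importance of the point. It does not explain the counts.

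Two stronger readings are tempting and should not be drawn.

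- A reader might infer that LDLT is confounded with study phase, since 300 of 660 LDLT patients (45%) and none of the 710 comparators would come from the Retrospective Study. But 660 and 710 are inputs to a simplified power calculation. The analysis in Section 4.2.5 is a repeated-measures model from donor evaluation in patients with and without LDLT, and it excludes no Retrospective non-recipients.
- A reader might infer that the chance of missing a 5-day difference is 13% and not 5%. That holds only if the comparison is confined to the Cohort Study, which the document does not establish.

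**Conclusion.** The point holds as an unexplained mismatch of inputs. The 95% follows correctly from 660 against 710, but that pairing is not a population the protocol defines. On a consistent population the power for 5 days is 98.5% (pooled) or 87% (Cohort only). The stated figure is conservative in the first case and about 8 points too high in the second.

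These figures rest on the protocol's own SD of 25, its anticipated counts and its simplified two-group design. The document does not decide between the two populations. Adequate power is not in doubt at these assumptions, and no fault in the planned analysis has been shown.

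**What to change.** In Section 4.2.4, state which study or studies supply both groups for the hospitalization comparison, and restate the power accordingly:

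- both studies: 660 LDLT against 1,210 non-LDLT, 98.5% power for 5 days, with study of origin added as an adjustment in the Section 4.2.5 model; or
- Cohort Study only: 360 against 710, 87% power for 5 days.

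If the two groups are meant to come from different sources, say so and give the reason. The cost is a sentence and a corrected figure, plus one covariate if the studies are pooled. Recruitment targets need not change.

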#### 4.2.5. Statistical Analysis

Survival from date of surgery for LDLT versus DDLT transplant will be compared using
Cox regression, adjusted for prognostic variables. The distributions of time from
transplant to rejection episode, or graft failure, between LDLT and DDLT transplant will
be similarly compared.

751

752 Initial analysis of LDLT recipient post-operative complications will be descriptive. We 753 will report the proportions of donors with complications such as bile leak, primary non-754 function, graft failure, pneumonia, and urinary tract infection, as well as any complication 755 requiring hospital admission, re-operation, or other intervention. Confidence intervals 756 will be included with all estimates. We will also report follow-up outcomes including 757 wound healing, pain medications, blood laboratory values, and the proportion of patients 758 who returned to work/school. Some attempt will be made to correlate complications with 759 patient characteristics and operative procedures, but any such analyses will be limited by

760 the quality of available data.

761 In addition, a comparison of LDLT complications with complications following DDLT

will be made. Depending on the type of complication (event occurrence, time to event, or

continuous outcome), a comparison of the events between LDLT and DDLT transplants

will be made using logistic regression, Cox regression, or ordinary regression,

- respectively, each adjusted for other predictive variables as needed.
- 766

Resource utilization, particularly hospitalization (number of hospitalizations and number
of hospital days) will be compared for those with and without LDLT using a repeated
measures generalized linear model analysis starting at the time of donor evaluation. In
addition, a comparison of hospitalization outcomes after LDLT versus DDLT will be

- made. Quality of life outcomes will be subscale scores calculated as weighted sums of
- ordinal variables, and can be analyzed as continuous variables. For comparing post transplant quality of life for LDLT versus DDLT, we will use repeated measures
- regression. Treatment differences as well as treatment by time interactions will be tested.
- 775

# 4.3. Primary Aim 3: To determine the short and long term health and QOL impact of donation, including (a) morbidity after liver donation, and (b) long term health-related QOL of donors compared to a control population.

- This study addresses the inadequacy and incompleteness of existing data to sufficiently
- 780 gauge the risk to the donor. Unanswered questions exist regarding the morbidity risks to Revised Cohort Protocol 031006 Page 19 of 56

781 782 783 784 785	the donor, for example: the risk that the donor will be left with inadequate hepatic reserve, the risk of biliary complications and other long-term consequences of hepatic resection. Information about quality of life and health status after adult-to-adult liver donation is even scantier; with no long-term prospective studies reported.
786 787 788 789	The analyses of these questions are critical in helping prospective donors make a true informed consent based on accurate assessment of long-term medical and psychological risks and benefits associated with LDLT.
790 791 792 793 794 795 796	Concerns exist regarding psychological and psychosocial problems as a result of donation that may not be adequately recognized by the transplant team. Although these concerns are largely based on anecdotes, it is an obligation of transplant programs to recognize these problems and to prevent or treat them effectively. Although various aspects of quality of life are important, there are specific post-donation concerns, including depression, sense of abandonment, body image, and sexual function. Instruments that adequately capture information on these issues will be administered to the donors.
797 798 799 800	Many hypotheses regarding donor outcomes and quality of life can be considered. Here are a few examples:
800 801 802 803 804 805 806 807 808 809 810 811 812 813 814	
 
Donor satisfaction will be related to both the medical and quality of life experiences of the recipient. This linkage will be greater for spouses.
 
Pre-donation, donor physical and mental QOL will be above the norm of the general population. One or more years post-donation, donor QOL will remain in the normal range of the population.
 
Donors with strong social support will feel less of a sense of abandonment.
 
Donors with a better understanding of the risks of the procedure will have greater acceptance post-donation.
 
Donors will have comparable QOL post-donation compared with controls who did not donate.
 
Sexual satisfaction and comfort with body image will be more positive for those with strong social support and a better understanding of their post-operative course.
 

815

#### 4.3.1. Study Methods

This analysis will compare LDLT donors to a donor control group who underwent 816 817 evaluation for donation but did not donate. Patients who are accepted as candidates for 818 donation will be provided information regarding A2ALL and invited to participate in the 819 donor cohort. Morbidity after liver donation will be studied by analyzing intraoperative 820 data, rate and severity of complications, number of post-operative hospitalizations and emergency room visits, and incidence of liver failure leading to the donor's listing for 821 822 transplantation. Donor quality of life will be assessed through the use of validated 823 questionnaires, including: 1) Life Orientation Test (LOT Optimism Scale), Appendix D, 2) Mini International Neuropsychiatric Interview (MINI) [Modules: Dysthymia, 824 825 Depression, Suicide, Anxiety, Post-traumatic Stress Disorder, Alcohol Dependence, Hypomania/mania, Generalized Panic Disorder and Substance Dependence], Appendix 826

827 E, 3) Medical Outcomes Study Short Form-36 (SF-36), Appendix F and 4) Brief McGill

828 Pain Survey, Appendix G, given at enrollment and post-donation at months 3, and 12,

829 and annually thereafter. The A2ALL Donor Survey, Appendix H, will also be

830 administered at enrollment, post-donation months 3 and 12 and annually thereafter.

831 Additionally, the McGill Pain Survey will be administered at Week 1 and Month 1. For

- 832 each time point, the goal is to have the questionnaire administered within a window of  $\pm$
- 833 1 month of the target date.
- 834

835 Retention of living liver donors and donor controls is essential for the success of the study. The Data Coordinating Center will be closely tracking the progress of both donors

836

837 and donor control subjects throughout the study. Regular reports will be maintained and shared with the Steering Committee and DSMB to monitor long-term participation.

838 839

840 Donors and donor controls will be offered \$25 compensation for each completed visit 841 after the 3 month post-donation visit (starts with the 12 month post-donation visit).

842

843 Anecdotally, transplant professionals have heard reports that donors feel "abandoned" by 844 the transplant team post-operatively. A2ALL centers will make post-operative check-in 845 calls to post-operative donors within the first four weeks after donation a standard of care 846 so that satisfaction levels regarding transplant team post-operative interactions can be 847 assessed in an unbiased manner via questionnaires.

848

849 For LDLT donors who are recruited from the A2ALL Retrospective Study, quality of life 850 will be assessed at enrollment, and then at the subsequent times post-donation following 851 the schedule above.

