468 469 470 471 472 473 474 475 476 477	
 
Physical examination: including weight, blood pressure, etc.
 
Routine laboratory assessment: blood will be drawn to obtain values for the following tests: multichannel automated liver function tests, serum sodium, albumin, AFP, creatinine, and coagulation panels
 
Blood sample for NIDDK Biosample Repository
 
Quality of life interval assessments at 3, 6, and 12 months and annually thereafter
 
Liver MRI/contrast CT at Month 3 only.
 
Recipients of a DDLT from an HCV-antibody positive donor must have HCV genotyping done at 3 months post-transplant
 

478 479	Post-transplant Interval Assessments – HCV-infected Recipients:
480	In addition to the assessments listed above, HCV-infected recipients will undergo the following assessments at the following time points:

483	• Week 1, Month 1, Month 3, Year 1, 2, and 3: HCV RNA quantitative or qualitative
484	analysis
485	• Month 3, Year 1, 2 and 3: Liver biopsy
486	• Month 3, Year 1, 2 and 3: Tissue sample for NIDDK Biosample Repository
487	
488	Post-transplant Interval Assessments – Subjects with HCC:
489	
490	In addition to the assessments listed above for all recipients, recipients with HCC will
491	undergo the following assessments at Months 6, 12, 18 and 24:
492	
493	• Serum AFP (at month 18 in addition to AFP's done at interval assessments for all
494	recipients)
495	• Abdominal MRI/contrast CT: at months 6, 12 and 24 only.
496	
497	Subjects Showing Signs and Symptoms of Allograft Rejection:
498	
499	Subjects showing signs and symptoms of allograft rejection will undergo a liver biopsy
500	with analysis to confirm the diagnosis of rejection. A biopsy will be performed to
501	confirm each rejection episode. A tissue sample from these biopsies will also be sent for
502	storage at the NIDDK Biosample Repository.
503	
504	Post-Donation Assessments – Donors:
505	
506	The following assessments will be performed for donors at Week 1, and Months 1, 3, and
507	12, and annually thereafter until the study is complete or the donor reaches a study
508	endpoint or is lost to follow-up:
509	
510	• Routine laboratory assessment: blood will be drawn to obtain values for the
511	following tests: multichannel automated liver function tests, albumin, creatinine,
512	coagulation panels, white blood cell count, hemoglobin, ferritin, platelets, BUN
513	Blood sample for NIDDK Biosample Repository
514	• Liver MRI/contrast CT at month 3 only

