515	• Quality of life assessment: limited to a pain survey at Week 1 and Month 1 for
516	donors. Donor and donor controls will undergo the full battery of QOL assessments
517	at Months 3, 12 and annually thereafter.
518	• Informed consent assessment (satisfaction with treatment): at Months 1, 3, and 12,
519	and annually thereafter
520	• Informed consent assessment (motivation): at Week 1, Months 3 and 12, and annually
521	thereafter.
522	• Donor controls will be asked to complete the QOL, Informed Consent and data
523	collections. No diagnostic, imaging or invasive procedures will be performed once
524	the decision not to donate has been made.
525	

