- 947 pooled to compare with the control group. If the two donor groups are not similar, they 948 will be analyzed as separate groups. We could then estimate any change in donor quality
- of life over calendar time, or by experience at the transplant center, due to improvements
- 950 in transplant methods or surgeon skill.
- 951

The analysis of pain scores will parallel the repeated measures analysis described above.

However, at each time point we will also collect data on the patient's expected future

pain. We will compare the predicted future pain with the pain score actually obtained at

- 955 the next questionnaire completion. In addition to the standardized scales, individual
- 956 questions from the A2ALL Donor Survey will also be analyzed, primarily using
- 957 descriptive statistics. Covariate predictors of some of these outcomes may be
- 958 investigated using linear or logistic regression.
- 959

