#### 2139 Appendix B: Schedule of Donor Visits, Tests and Assessments

\*Donor controls will not have any laboratory, clinical or blood testing performed after decision not to donate has been made. They will continue to be followed

for data collection, QOL and informed consent assessments at the visits listed in the above schedule

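### The ±1 month questionnaire window cannot separate the donor pain surveys at Week 1 and Month 1: every post-donation day allowed for Week 1 is also allowed for Month 1

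*Protocol*

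**What the plan says.** Protocol section 4.3.1 (Study Methods, Primary Aim 3) schedules the donor quality-of-life questionnaires at enrollment, Months 3 and 12, and yearly after that. It then adds two early pain surveys: "Additionally, the McGill Pain Survey will be administered at Week 1 and Month 1". The next sentence sets the timing standard: for "each time point, the goal is to have the questionnaire administered within a window of" ±1 month of the target date. It makes no exception for the two surveys just named.

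The donor schedule in section 4 (Post-Donation Assessments – Donors) lists Week 1 and Month 1 among the post-donation time points: "The following assessments will be performed for donors at Week 1, and Months 1, 3, and" 12, then yearly. At the two early visits quality of life is "limited to a pain survey at Week 1 and Month 1 for" donors, and controls join for the full battery from Month 3. Neither this list nor the Appendix B schedule gives a narrower window.

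Section 4.3.5 says of the pain data: "The analysis of pain scores will parallel the repeated measures analysis described above".

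**The concern.** A visit window should tie a score to its time point. A one-month tolerance is reasonable for visits that are months or a year apart. It does not suit two surveys about three weeks apart, the first of them only a week after major surgery.

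After the day of donation, Week 1 and Month 1 are the only scheduled pain surveys before Month 3, and Aim 3 covers short-term as well as long-term impact. If a survey taken in week 5 counts as an on-time Week 1 score, the Week 1 mean mixes pain in the first days with pain a month later, and the Week 1 to Month 1 change loses meaning. If survey dates are recorded, an analyst can relabel a late score, but cannot recover the week-1 pain that was not measured then.

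This is not a detail left to a statistical analysis plan. The protocol states a rule for when data are collected, and for these two time points the rule does not fit.

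**Working it through.** **Inputs.**
- Targets: Week 1 = day 7 and Month 1 = about day 30 after donation (section 4.3.1; section 4 donor schedule).
- Half-width: 1 month (section 4.3.1). The protocol does not define a month in days; 30 is the base case, with 28 and 31 as the range.
- Both are post-donation assessments, so only day 0 onward counts.

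**Formula.** Window = target ± m, cut at day 0, where m is the month in days.

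**Base case, m = 30.**
- Week 1: 7 − 30 = −23, cut to 0; 7 + 30 = 37. Window day 0 to 37, which is 38 days.
- Month 1: 30 − 30 = 0; 30 + 30 = 60. Window day 0 to 60, which is 61 days.
- Shared: day 0 to 37, which is 38 of 38 Week 1 days and 38/61 = 62% of the Month 1 days.
- Distance between targets: 30 − 7 = 23 days, less than the half-width of 30.

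**Other month lengths (Month 1 target = m).**

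| Month length | Week 1 window | Month 1 window | Week 1 days also in Month 1 |
|---|---|---|---|
| 28 days | 0 to 35 | 0 to 56 | 36 of 36 |
| 30 days | 0 to 37 | 0 to 60 | 38 of 38 |
| 31 days | 0 to 38 | 0 to 62 | 39 of 39 |

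Both windows start at day 0, and 7 + m is at most 2m whenever m is at least 7, so the result does not depend on the month length. A calendar-month check over every donation date from 2004 to 2008 found no exception.

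**Later visits, m = 30.** Month 3: 90 ± 30 = day 60 to 120, which shares only day 60 with Month 1. Month 12: 365 ± 30 = day 335 to 395, which shares nothing with Month 3. The full overlap is confined to the two early surveys.

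**What would separate them.** A common half-width h keeps the windows apart if 7 + h < 30 − h, so h < 11.5. At h = 11, Week 1 ends on day 18 and Month 1 starts on day 19. At h = 12, they end and start on days 19 and 18 and overlap.

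**Aim 3 power, as a check on reach.** Section 4.3.4 states 87% for an effect size of 0.20 with 360 donors and 710 controls. By normal approximation, 0.20 × √(360 × 710 / 1070) = 3.09; 3.09 − 1.96 = 1.13; power ≈ 0.871. The stated figure reproduces, and the visit window does not enter it.

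**The case against.** The best reply is that the sentence is a goal for administering questionnaires, not a rule for assigning scores to visits. The protocol requires two separate surveys with different targets, and it lists them with laboratory tests and repository blood at the same Week 1 and Month 1 visits. In practice those visits will often fix the timing, and the Manual of Operations, which is not at hand, may say more. This stands and limits the size of the point: 38 of 38 counts permitted days, not expected mislabelled surveys. It does not remove the point, because this is the only timing standard the protocol gives for these surveys. One could also read the questionnaire as the full battery only, but the sentence covers each time point and directly follows the one adding Week 1 and Month 1.

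Three stronger readings are tempting and not supported.
- A reader might infer that one survey can serve both visits. Overlapping tolerances do not merge two separately scheduled surveys.
- A reader might infer that the comparison of predicted with actual pain in section 4.3.5 ("We will compare the predicted future pain with the pain score actually obtained at" the next completion) loses its intended interval. That comparison is defined by the order of completion and fixes no interval, and the instrument that would state the prediction period is not shown.
- A reader might infer from the Appendix B footnote, which follows controls "for data collection, QOL and informed consent assessments at the visits listed in the above schedule", that controls also take the early pain surveys. Section 4 is more specific and limits them to donors. A repeated-measures model can take visits that only donors have.

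**Conclusion.** The point holds and is minor. As written, the ±1 month goal does not distinguish the Week 1 and Month 1 pain surveys: every post-donation day acceptable for Week 1 is acceptable for Month 1, and a survey up to 30 days past the Week 1 target (day 37) counts as on time. This assumes that the sentence applies to the two early surveys, as its wording and position indicate, and that only days from donation on count. It does not depend on the month length.

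The effect is limited to how sharply early donor pain is described. How often surveys would in fact be late cannot be judged from the protocol. The donor-control contrasts from Month 3 on and the 87% power are unaffected.

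**What to change.** In section 4.3.1, keep ±1 month for Month 3 and later, and give the two early surveys their own windows that do not overlap. One example is Week 1 at days 4 to 10 (day 7 ± 3) and Month 1 at days 23 to 37 (day 30 ± 7). Any common half-width of at most 11 days also works; the exact limits are for the investigators to choose.

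The cost is one short wording change and no added survey. The downside is that some early surveys taken late will be out of window; with the example limits, days 11 to 22 belong to neither visit. Such surveys should be kept and analysed by their actual date, not dropped or relabelled to the nearest visit.
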